1.2.3 Safety Concerns [17]

1. Angioedema

There have been post-marketing reports of angioedema in patients during initial and chronic treatment with pregabalin. Specific symptoms included swelling of the face, mouth (tongue, lips, and gums), and neck (throat and larynx). There were reports of life-threatening angioedema with respiratory compromise requiring emergency treatment. Pregabalin should be discontinued in patients with these symptoms.

Exercise caution when prescribing pregabalin to patients who have had a previous episode of angioedema. In addition, patients who are taking other drugs associated with angioedema (e.g., angiotensin converting enzyme inhibitors [ACE-inhibitors]) may be at increased risk of developing angioedema.

2. Hypersensitivity

There have been post-marketing reports of hypersensitivity in patients shortly after initiation of treatment with pregabalin. Adverse reactions included skin redness, blisters, hives, rash, dyspnea, and wheezing. Discontinue pregabalin immediately in patients with these symptoms.

3. Withdrawal of Antiepileptic Drugs (AEDs)

As with all AEDs, withdraw pregabalin gradually to minimize the potential of increased seizure frequency in patients with seizure disorders. If pregabalin is discontinued, taper the drug gradually over a minimum of 1 week.

4. Suicidal Behavior and Ideation

Antiepileptic drugs (AEDs) including pregabalin, increase the risk of suicidal thoughts or behavior in patients taking these drugs for any indication. Monitor patients treated with any AED for any indication for the emergence or worsening of depression, suicidal thoughts or behavior, and/or any unusual changes in mood or behavior.

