1. Immediately removed from the study and discontinue the drug using the taper schedule outlined in section 8.1 (renal dose tapering).

2. Urgently referred to the counseling service at the Abramson Cancer Center.

3. Escorted to PEEC (Psychological Emergency Evaluation Center) if a patient reports suicidal thoughts and a plan to commit suicide that they intend to carry out.

Subjects who develop 1) grade 3 or GREATER thrombocytopenia; or 2) experience an unanticipated event (such as those outlined in the pregabalin package insert) will be directed to reduce their dose by 50% starting that day. The subject will then decrease the study drug by 1 pill per day thereafter until complete discontinuation. Patients titrating over the weekends will be directed to call the Radiation Oncologist on call if they experience any new side effects.

Approximately four weeks following completion of radiation treatments, study subjects will taper the pregabalin dose for a minimum of one week before stopping. This taper will follow a reverse schedule of the titration: 75mg twice daily for three days, 75mg once a day for three days, then no medication on the seventh day. The rate of taper may be modified by the PI or treating physician/NP as per the subject's clinical situation and PI or physician/NP's discretion.

Study subjects with persistent mucositis pain responding to pregabalin may continue to take the pregabalin for up to 4 additional weeks on study. After this point, any additional pregabalin administration will be off-study and solely at the discretion of the treating physician/NP. At that time, the cost of the medication will become the responsibility of the patient (or their medical insurance).

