At screening, any clinically significant abnormality should be recorded as a preexisting condition. At the end of the study, any new clinically significant findings/abnormalities that meet the definition of an adverse event must also be recorded and documented as an adverse event.

Post-study Adverse Event

All unresolved adverse events should be followed by the investigator until the events are resolved, the subject is lost to follow-up, or the adverse event is otherwise explained. At the last scheduled visit, the investigator should instruct each subject to report any subsequent event(s) that the subject, or the subject's personal physician/NP, believes might reasonably be related to participation in this study.

Abnormal Laboratory Values

A clinical laboratory abnormality should be documented as an adverse event if any one of the following conditions is met:

- The laboratory abnormality is clinically significant and not otherwise refuted by a repeat test to confirm the abnormality
- The abnormality suggests a disease and/or organ toxicity
- The abnormality is of a degree that requires active management; e.g. change of dose, discontinuation of the drug, more frequent follow-up assessments, further diagnostic investigation, etc.

Renal dose Taper

In view of dose-dependent adverse reactions and since LYRICA is eliminated primarily by renal excretion, adjust the dose in patients with reduced renal function. Base the dose adjustment in patients with renal impairment on creatinine clearance (CLcr), as indicated in Table 1. To use this dosing table, an estimate of the patient's CLcr in mL/min is needed. CLcr in mL/min may be estimated from serum creatinine (mg/dL) determination using the Cockcroft and Gault equation:

$$CLCr = \frac{[140 - age (years)] \times weight (kg)}{72 \times \text{ serum creatinine (mg/dL)}} (\times 0.85 \text{ for female patients})$$

Next, refer to the Dosage and Administration section to determine the recommended total daily dose based on indication, for a patient with normal renal function (CLcr \geq 60 mL/min). Then refer to Table 1 to determine the corresponding renal adjusted dose.

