(For example: A patient initiating LYRICA therapy for postherpetic neuralgia with normal renal function ($CLcr \ge 60$ mL/min), receives a total daily dose of 150 mg/day pregabalin. Therefore, a renal impaired patient with a CLcr of 50 mL/min would receive a total daily dose of 75 mg/day pregabalin administered in two or three divided doses.)

For patients undergoing hemodialysis, adjust the pregabalin daily dose based on renal function. In addition to the daily dose adjustment, administer a supplemental dose immediately following every 4-hour hemodialysis treatment (see Table 1).

Table 1. Pregabalin Dosage Adjustment Based on Renal Function Creatinine Clearance (CLcr) (mL/min)	Total Pregabalin Daily Dose (mg/day)*			Dose Regimen			
≥60	150	150 300 450 600 BID or TID					
30–60	75	150	225	300	BID or TID		
15–30	25-50	75	100-150	QD or BID			
<15	25	25-50	50-75	75	QD		
Sup	plementary	dosage fo	llowing hemo	odialysis (mg	z)†		
Patients on the 25 mg QD regimen: take one supplemental dose of 25 mg or 50 mg Patients on the 25–50 mg QD regimen: take one supplemental dose of 50 mg or 75 mg Patients on the 50–75 mg QD regimen: take one supplemental dose of 75 mg or 100 mg Patients on the 75 mg QD regimen: take one supplemental dose of 100 mg or 150 mg							

In this protocol, patients with a baseline GFR < 30 will be ineligible. Patients with GFR of 30-60ml/min (as determined by laboratory evaluation one week after chemotherapy and hydration) will have drug dose reduced to 75 mg, twice daily for the remainder of the study. Patients with a GFR < 30 will be removed from the study (also listed as exclusion criteria). Potential side effects associated with a quick taper far out weight the side effects of depression.

Hospitalization, Prolonged Hospitalization or Surgery

Any adverse event that results in hospitalization or prolonged hospitalization should be documented and reported as a serious adverse event unless specifically instructed otherwise in this protocol. Any condition responsible for surgery should be documented as an adverse event if the condition meets the criteria for and adverse event.

Neither the condition, hospitalization, prolonged hospitalization, nor surgery are reported as an adverse event in the following circumstances:

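### Section 5.2 sends positive depression screens to a taper schedule that section 8.1 does not contain, and its step-down for package-insert events conflicts with the immediate stop for hypersensitivity in section 1.2.3

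*Combined protocol and SAP*

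**What the plan says.** Section 5.2 (Treatment Regimen) removes any patient who scores 10 or higher on the depression screen, or gives a non-zero answer to its question 5. That patient must "discontinue the drug using the taper schedule outlined in section 8.1 (renal dose tapering".

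Section 8.1, under Renal dose Taper, starts from the need to "adjust the dose in patients with reduced renal function" and reproduces the label's table of doses by creatinine clearance. It adds two trial rules: patients with a GFR of 30-60 "will have drug dose reduced to 75 mg, twice daily for the remainder of the study", and those below 30 leave the study. Its only mention of depression is one sentence: "Potential side effects associated with a quick taper far out weight the side effects of depression".

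Section 5.2 has a second stopping rule. Subjects who develop grade 3 or greater thrombocytopenia, or who "experience an unanticipated event (such as those outlined in the pregabalin package insert) will be directed to reduce their dose by 50" percent, start that cut the same day. "The subject will then decrease the study drug by 1 pill per day thereafter until complete discontinuation".

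Section 1.2.3 (Safety Concerns), item 2, says of hypersensitivity: "Discontinue pregabalin immediately in patients with these symptoms".

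The only dated schedule that reaches zero is the end-of-treatment taper in section 5.2: "This taper will follow a reverse schedule of the titration: 75mg twice daily for three days, 75mg once a day for three days", with nothing on day seven.

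**The concern.** Section 5.2 is where staff look when the drug has to be stopped, and section 1.2.3 itself refers them there for tapering. Two of its instructions fail when followed literally. A patient just removed for depression or suicidal thoughts is sent to a section from which no stopping schedule can be read, although section 1.2.3 says this drug class raises the risk of suicidal thoughts. A patient with suspected hypersensitivity gets an immediate stop from one section and a step-down from another. What is at stake is patient safety and consistent conduct, not the statistical estimate.

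**Working it through.** No planned figure needs reproducing here; the check sets the sections side by side and works out the doses.

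**1. Does section 8.1 reach zero?** The target dose in section 5.2 is 150 mg twice daily, so 2 x 150 = 300 mg/day. In section 8.1's Table 1, clearance of 60 or above keeps 300 mg/day and clearance of 30-60 gives 150 mg/day. The lowest legible entry anywhere in the table is 25 mg/day. No durations are given, so section 8.1 contains no step to zero. By contrast, the section 5.2 reverse titration gives (2 x 75) x 3 days + 75 x 3 days = 450 + 225 = 675 mg over 6 dosing days, and zero on day 7.

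**2. Does the step-down cover hypersensitivity?** Section 1.2.3 cites reference 17, the pregabalin prescribing information, and lists hypersensitivity. By the protocol's own sourcing it is therefore a package-insert event. The parenthetical in section 5.2 names such events as examples of its trigger. The one-week tapers in section 1.2.3 (item 8) and under How to Withdraw Subjects state no allergic exception. An explicit order to stop at once appears for 1 of the 13 items in section 1.2.3.

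**3. How much drug follows a reaction?** Start at 300 mg/day. The 50% cut allows 150 mg that day, then one pill less each day. Capsule strength is not stated; 75 and 150 mg are assumed because the regimen uses those doses. Only doses after the reaction are counted, for a patient on active drug.

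| Unit assumed | Timing of reaction | Doses after it (mg, by day) | Total | Dosing days |
|---|---|---|---|---|
| 150 mg | after morning dose | 0, 0 | 0 mg | 0 |
| 150 mg | before morning dose | 150, 0 | 150 mg | 1 |
| 75 mg | after morning dose, evening dose omitted | 0, 75, 0 | 75 mg | 1 |
| 75 mg | after morning dose, evening dose halved | 75, 75, 0 | 150 mg | 2 |
| 75 mg | before morning dose | 150, 75, 0 | 225 mg | 2 |

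Smaller listed capsules lengthen it, again with the reaction before the morning dose. With 50 mg: 150 + 100 + 50 = 300 mg over 3 days. With 25 mg: 150 + 125 + 100 + 75 + 50 + 25 = 525 mg over 6 days. Section 1.2.3 gives 0 mg throughout.

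**4. Can the step-down be carried out?** Section 1.2.1 issues the 20 mg/mL solution to patients who are NPO or cannot swallow pills. For them, one pill per day has no meaning. The equivalents would be 75/20 = 3.75 mL and 150/20 = 7.5 mL. On titration days 1-2 (75 mg nightly), half the dose is 37.5 mg. Every listed capsule is a multiple of 25 mg, so only the solution can supply it (37.5/20 = 1.875 mL).

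**5. Do dizziness and sedation fall under the same trigger?** Section 5.2 lets these patients delay escalation, reduce the dose and continue. Dizziness and somnolence are also among the events section 1.2.3 takes from the prescribing information, so the parenthetical could send them to full discontinuation instead. The text does not settle which applies.

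**6. Does any estimate change?** Section 7.7 analyses every subject who received at least one dose and keeps dropouts in the population. The section 5.2 sentence about inclusion in the analyses concerns patients who miss the goal dose and stay on study, so section 7.7 alone supports this for removed patients. Data collected after removal depend on their consent to follow-up.

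**The case against.** The strongest reply is that no patient is left unprotected. A positive screen brings a meeting with a physician or NP. Item 8 of section 1.2.3 points to section 5.2 for taper details, and How to Withdraw Subjects gives a taper of at least one week at clinician discretion. During titration, when an early allergic reaction is most likely to be seen, staff assess patients daily and report to the PI, and an on-call radiation oncologist covers weekends. For hypersensitivity, a symptom-specific order would ordinarily prevail over a general catch-all, and a reader could hold that labelled events are not unanticipated at all.

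Most of this stands as mitigation. It does not repair the text. Section 5.2 names section 8.1, not the fallbacks, for depression. The parenthetical expressly brings labelled events into the trigger. The permission to vary the taper rate sits in the end-of-treatment paragraph and does not clearly reach event-driven stopping. The investigator may withdraw a patient on safety grounds, but the withdrawal procedure then prescribes the same gradual taper.

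Three stronger readings are tempting and unsupported. A reader might infer that the safeguard against hypersensitivity is missing; it is present in section 1.2.3 and contradicted in section 5.2. A reader might see the same conflict for angioedema; section 1.2.3 says to discontinue but gives no timing, so the text is silent there rather than contradictory. A reader might treat the fast thrombocytopenia taper as a further error; item 12 of section 1.2.3 shows that it is deliberate.

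**Conclusion.** The point holds as a safety-wording fault in two instructions of section 5.2, and it should be fixed. The section 8.1 reference fails outright, because there is no stopping schedule at the place cited. The hypersensitivity conflict rests on the natural reading of the package-insert parenthetical. Its size is uncertain: 0 to 225 mg over 0 to 2 dosing days under the 75 or 150 mg assumption, and up to 525 mg over 6 days with 25 mg capsules. At the lower end the step-down is no different from an immediate stop, so the case rests on the contradiction and not on a particular dose. The planned descriptive analysis is unaffected.

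**What to change.** Amend section 5.2:

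- **Depression or suicidality.** Replace the section 8.1 reference with the reverse-titration taper already in section 5.2, entered at the step at or below the patient's current dose, with the rate at clinician discretion as under How to Withdraw Subjects. The entry rule matters: screening is daily during week 1, and a patient on 75 mg nightly sent to the first step would go from 75 to 150 mg/day. That patient should start at 75 mg once daily. Since that step lasts three days, the text should say whether it is to be held longer to meet the one-week minimum.
- **Hypersensitivity.** State that suspected hypersensitivity means immediate discontinuation without taper, overriding the step-down and the one-week tapers in section 1.2.3 and How to Withdraw Subjects. Add angioedema if the investigators confirm it.
- **Trigger.** Delete the package-insert parenthetical and state that dizziness and sedation follow the delay-or-reduce rule. Do not add a grade or relatedness threshold: the documents give no basis for one, and it would narrow an existing stopping trigger.
- **Units.** Write step-downs in mg with mL equivalents for the solution (75 mg = 3.75 mL; 150 mg = 7.5 mL).

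Keep the fast taper for grade 3 or greater thrombocytopenia. The cost is a wording-only amendment, with no new procedures, visits or data.

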5.2 Treatment Regimen

Study subjects will self-administer oral preparation of pregabalin or matching placebo in twice daily dosage. Study subjects may use capsule form or solution, depending on medical necessity.

All study subjects will start taking 75mg of pregabalin nightly starting on the first day of radiation treatments. The dose will be increased to 75mg twice daily on day 3 and subsequently to 150mg twice daily on day 5.

Study subjects randomized to the treatment arm will continue to take 150mg of pregabalin twice daily for the duration of their radiation treatments until approximately their one month follow up visit. Subjects will be instructed at their follow up visit on how to taper the study drug.

Subjects randomized to the placebo arm will receive capsules and/or liquid that looks identical to the treatment arm. Subjects will titrate and taper in a fashion identical to the treatment arm.

At the discretion of the treating physician/NP, the interval between increasing dosage may be prolonged to a maximum of 4 days or the dosage reduced after the goal dose has been reached. Participants reporting excessive sedation or dizziness will be allowed to delay dose escalation. If a patient is not able to reach or maintain the goal dose at any point during the study (such as due to an adverse event at least possibly related to the study drug), the patient may continue on study and will be included in the analyses. The dose reached/dose

CONFIDENTIAL

Page 14

reduction will be recorded by the treating physician/NP with annotation of the rationale for the decision to maintain at that dose.

During titration, patients will be assessed daily by designated study staff before or after their daily radiation treatment in order to discuss/report with/to the PI any adverse events associated with the study drug.

Patients will be screened for suicidal ideation by designated study staff at baseline, daily during week 1 titration of the study drug and on a weekly basis during the study period until chemotherapy and radiation therapy are completed. Patients will be screened for depression again at the 1 month inspection visit. All patients will be screened using the Depression Screening assessment (appendix H).

Patients scoring a 10 or higher or reporting anything other than a 0 on question # 5 will meet with a physician/NP and will be:

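### The default end-of-study taper in section 5.2 is built for a 150 mg twice-daily start; followed unmodified from 75 mg twice daily, it falls short of the protocol's one-week minimum

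*Combined protocol and SAP*

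**What the plan says.** Section 5.2 sets a rule, a default and a discretion clause, in that order. About four weeks after radiotherapy ends, "study subjects will taper the pregabalin dose for a minimum of one week before stopping". Then: "This taper will follow a reverse schedule of the titration", with the steps "75mg twice daily for three days, 75mg once a day for three days, then no medication on the seventh day". Then: "The rate of taper may be modified by the PI or treating physician/NP as per the subject's clinical situation".

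The titration being reversed starts at 75 mg at night and ends at the goal dose: "The dose will be increased to 75mg twice daily on day 3 and subsequently to 150mg twice daily on day 5".

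Not every patient will be on the goal dose when the taper begins. Section 1.2.2 (Pharmacokinetics) and section 8.1 (Renal dose Taper) lower patients with GFR 30–60 mL/min, measured a week after chemotherapy, to 75 mg twice daily until the study ends. Section 5.2 separately allows "the dosage reduced after the goal dose has been reached" at the clinician's discretion, and keeps such patients on study and in the analysis.

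For the placebo arm, "Subjects will titrate and taper in a fashion identical to the treatment arm". On timing, "Subjects will be instructed at their follow up visit on how to taper the study drug".

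The one-week minimum also appears in section 1.2.3 (items 3 and 8) and under Early Withdrawal of Subjects. Item 8 of 1.2.3 refers the reader to 5.2 for the taper.

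**The concern.** A schedule that reverses a titration to 150 mg twice daily fits patients who are on that dose. Its first step, 75 mg twice daily, is exactly the maintenance dose of the renal group. For those patients the taper begins on paper three days before any dose changes. The group is foreseeable: platinum chemotherapy is an entry requirement, only creatinine clearance below 30 mL/min is excluded, and the protocol plans the GFR check after chemotherapy.

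What is at stake is the protection that 1.2.3 item 8 describes. Some patients reported insomnia, nausea, headache and diarrhea after abrupt or rapid discontinuation. Patients take the drug themselves, and the taper is taught at the follow-up visit, the last visit in the schedule of events. No scheduled visit follows at which a short taper would be noticed, although adverse events remain reportable for 30 days after the last dose.

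**Working it through.** This is a day count by starting dose.

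**Inputs.** Default steps and one-week minimum: section 5.2. Goal dose 150 mg twice daily = 300 mg/day: section 5.2. Renal dose 75 mg twice daily = 150 mg/day: sections 1.2.2 and 8.1. A reduced-dose day is a day on which some drug is taken, but less than the starting daily dose.

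| Taper day | Default (mg/day) | Against a 300 mg/day start | Against a 150 mg/day start |
|---|---|---|---|
| 1–3 | 150 | reduced by 150 | unchanged |
| 4–6 | 75 | reduced by 225 | reduced by 75 |
| 7 | 0 | stopped | stopped |

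**The plan's own figure, from 150 mg twice daily.** Reduced-dose days = 3 + 3 = 6. Adding the drug-free day, 6 + 1 = 7. This reproduces the stated week, provided the drug-free day is counted, as the protocol evidently does.

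**From 75 mg twice daily.** Reduced-dose days = 6 − 3 = 3. Adding the drug-free day, 3 + 1 = 4.

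**Shortfall against 7 days.** On the protocol's count, 7 − 4 = 3 days. If only dosing days count, 7 − 3 = 4 days.

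**Does another section supply the missing steps?** Section 8.1 carries the title Renal dose Taper, but its content is a table for adjusting the daily dose to creatinine clearance, plus the rule that puts GFR 30–60 on 75 mg twice daily. It gives no steps for stopping.

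**Check of the proposed steps, from 75 mg twice daily.** With 75 mg once daily on days 1–6 and none on day 7, reduced-dose days = 6, or 7 with the drug-free day. This matches the full-dose schedule and ends on the same calendar day.

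**Drug used.** Default: 3 × 150 + 3 × 75 = 675 mg. Proposed: 6 × 75 = 450 mg, or 7 × 75 = 525 mg with seven dosing days.

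**The case against.** The strongest reply is that section 5.2 already resolves this. The minimum comes first, the steps second and the discretion clause third. Being on half the goal dose is plainly part of a patient's clinical situation, and the minimum tells the clinician what an adapted schedule must achieve. The treating clinician knows the dose and records the reason for any discretionary reduction. This largely stands, and it is why the point is minor. It does not remove the point: the clause permits a change without requiring one, and the written steps, followed as they are, miss the rule that introduces them.

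Second, the protocol never defines the week as days below the current dose. That is true; it is my reading. But three days at an unchanged dose are hard to call tapering.

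Third, the clinical weight is small. Section 1.2.3 item 3 ties the minimum to seizure frequency in patients with seizure disorders, and a history of seizure is an exclusion. The default is still stepwise from 150 mg/day (150, 75, 0), and its first drop of 75 mg/day is smaller than the full-dose patient's first drop of 150 mg/day. Section 5.2 accepts a faster taper for thrombocytopenia and unanticipated events. No symptom rate is given, and at most 10 patients receive active drug. All of this stands.

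Fourth, a lower dose may need less taper. The protocol makes no such exception. Table 1 in 8.1 halves the dose at clearance 30–60 because elimination slows, so exposure may be similar to full dose. Slower clearance may equally soften the stop. The documents do not settle this.

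A reader might infer that the protocol obliges renal patients to stop too quickly, or abruptly. The documents do not support that: the schedule is a modifiable default, and it still steps down.

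**Conclusion.** The point holds as a minor safety inconsistency in the written default. From 75 mg twice daily, the unmodified schedule gives 3 reduced-dose days, or 4 with the drug-free day. That is 3 days short of one week on the protocol's own count, or 4 if only dosing days count.

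This assumes that the default is followed unchanged, that the patient is on 75 mg twice daily when the taper starts, and that a taper day is a day below the current dose. The documents do not say how many patients this would be, and they give no basis for estimating how many would have symptoms.

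Two further inferences should be resisted. One is that the full-dose schedule also fails because it has only six dosing days. The protocol offers those steps as its one-week taper, with the seventh day drug-free, and on that count they comply. The other is that the short taper could bias the primary endpoint. Section 3.4 records opioid use at the weekly visits and the follow-up visit, and the taper is taught at that follow-up visit. There is no effect on the endpoint or the planned descriptive analysis.

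**What to change.** Add one or two sentences to section 5.2: the taper starts below the patient's current dose and lasts at least one week. Give the 75 mg twice-daily case as an example: 75 mg once daily on days 1–6 and none on day 7. If the sponsor means the week to be dosing days, use seven days of 75 mg once daily and none on day 8. Apply identical steps to placebo, as 5.2 already requires. The sponsor chooses the final steps.

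Leave the 150 mg twice-daily schedule, the faster safety taper and the discretion clause as written. No new limit on clinician discretion is needed.

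The cost is the added text and a revised taper instruction sheet. No new capsule strength is needed. Drug use per affected patient falls from 675 mg to 450 mg, or to 525 mg with seven dosing days. The six-day version ends on the same calendar day as the default; the seven-day version ends one day later. The change moves the first reduction from day 4 to day 1. That brings the default into line with the stated minimum, though the documents do not show that it would reduce symptoms.
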